5.3. Duration of Therapy

In the absence of treatment delays due to adverse event(s), treatment may continue until one of the following criteria applies:

- Disease progression,
- Intercurrent illness that prevents further administration of treatment,

- Unacceptable adverse events(s),
- Patient decides to withdraw from the study, or
- General or specific changes in the patient's condition render the patient unacceptable for further treatment in the judgment of the investigator.

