13. STATISTICAL CONSIDERATIONS

13.1. Study Design/Endpoints

13.1.1. Phase I.

The phase I trial will use a 3+3 design with the MTD defined as the highest dose level such that <2 of 6 patients experience dose-limiting toxicity.

13.1.2. Phase II.

There is no standard therapy for differentiated thyroid cancer that is refractory to radioactive iodine. The best studied agent in this disease, doxorubicin, has an estimated response rate of 10%. Although cediranib has not been studied in thyroid cancer, a phase II study of the VEGF inhibitor motesanib diphosphate showed a median progression-free survival (PFS) of 40 weeks. Because we hypothesize that combination therapy will be more effective than single agent treatment, we will randomize in a 1:2 ratio, which should enhance recruitment. The randomization will be stratified by prior therapy with a VEGF-pathway inhibitor (yes vs. no) and performance status (0-1 vs. 2)

The primary endpoint will be PFS, which will be compared between the two treatment arms using a stratified logrank test. To determine the sample size, we noted that the median PFS in 93 patients with radioiodine-resistant thyroid cancer treated with motesanib diphosphate²⁵ was 40 weeks. We therefore assume a median of 40 weeks for the cediranib alone arm. In order to have 85% power to detect a 75% improvement in the median to 70 weeks with combination therapy (hazard ratio [HR]=1.75), 110 patients will be required (36 randomized to cediranib and 74 to cediranib plus lenalidomide), based on a one-sided test at the $\alpha=0.10$ significance level. This calculation assumes 1 year of accrual (9 patients per month) and 1.5 years of additional follow-up for a total study duration of 2.5 years. Kaplan-Meier³⁰ curves will be generated for each treatment arm and the median PFS times estimated using the Brookmeyer and Crowley method³¹. In addition to the logrank test, PFS in the two groups will be analyzed by fitting a Cox³² proportional hazards regression model, adjusting for prior VEGF inhibitor use, performance status, and other baseline risk factors. The goodness of fit of the Cox model and the appropriate functional form for continuous covariates will be assessed using graphical techniques, including inspection of martingale residual plots.

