13.4. Analysis of Secondary Endpoints

13.4.1. Phase I.

The objective response rate of cediranib in combination with lenalidomide in patients with iodine refractory, unresectable DTC who have evidence of disease progression within 6 months of study enrollment will be estimated. In addition, the toxicity, duration of response, progression free survival, and overall survival in patients with DTC treated with cediranib plus lenalidomide will be evaluated.

13.4.2. Phase II.

Overall survival (OS) rates will be estimated and compared between groups using methods similar to that described above for PFS. Response rates will be compared using a chisquare test followed by logistic regression analysis to adjust for covariates.

The percent change in tumor size from baseline to the end of cycle 2 (two months) will be compared between the two groups using a two-sample t test³³. The post-treatment total sum of lengths for a patient with a new lesion will be scored as $1.2 * \max(\text{pre-sum}, \text{post-sum})$ to ensure that the appearance of new lesions corresponds to a disease progression per RECIST criteria. In the event of any early deaths prior to two months, a nonparametric rank sum test will be used in place of the t test, with deaths ranked at the extreme end of the distribution.

Adverse events will be summarized by type and grade. Adverse event rates will be compared between the two treatment groups using a chisquare test for common toxicities and Fisher's exact test for less frequent events.

Repeated measures analysis of variance (RM ANOVA) will be performed to determine the effect of the treatments on serial measurements of TSH and thyroglobulin. It is hypothesized that these levels will decrease over time. Baseline tissue biomarker expression, scored as present or absent, of *B-RAF* and *RAS* mutations will be correlated with response rates using Fisher's exact test, and with PFS and OS by fitting a Cox proportional hazards regression model.

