13.5. Reporting and Exclusions

13.5.1. **Evaluation of toxicity.** All patients (Phase I and II) will be evaluable for toxicity from the time of their first treatment with cediranib or cediranib plus lenalidomide.

13.5.2. **Evaluation of response.** All patients included in the study (Phase I and II) will be assessed for response to treatment, even if there are major protocol treatment deviations or if they are ineligible. Each patient will be assigned one of the following categories: 1) complete response, 2) partial response, 3) stable disease, 4) progressive disease, 5) early

death from malignant disease, 6) early death from toxicity, 7) early death because of other cause, or 9) unknown (not assessable, insufficient data).

All of the patients who met the eligibility criteria (with the possible exception of those who received no study medication) will be included in the main analysis of the response rate. Patients in response categories 4-9 will be considered to have a treatment failure (disease progression). Thus, an incorrect treatment schedule or drug administration will not result in exclusion from the analysis of the response rate.

All conclusions will be based on all eligible patients. Subanalyses may then be performed on the basis of a subset of patients, excluding those for whom major protocol deviations have been identified (e.g., early death due to other reasons, early discontinuation of treatment, major protocol violations, etc.). However, these subanalyses will not serve as the basis for drawing conclusions concerning treatment efficacy, and the reasons for excluding patients from the analysis will be clearly reported. Data will be reported to CTEP using CDUS -Complete.

REFERENCES

1. National Cancer Institute. Surveillance, Epidemiology, and End Results (SEER) Program. <http://seer.cancer.gov/> Accessed 2009.
2. American Cancer Society. www.cancer.org/docroot/home/. Accessed 2009.

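### The crude adverse-event comparison in Section 13.4.2 confounds toxicity with time on treatment, for common toxicities that keep arising during therapy

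*Combined protocol and SAP*

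**What the plan says.** Section 13.4.2 has two sentences on toxicity. The first is descriptive: "Adverse events will be summarized by type and grade". The second sets the between-arm test: "Adverse event rates will be compared between the two treatment groups using a chisquare test for common toxicities". For rarer events the same sentence switches to the Fisher test. Although the text speaks of rates, chi-square and Fisher tests act on counts of patients with and without an event.

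Section 13.5.1 fixes when observation starts: "All patients (Phase I and II) will be evaluable for toxicity from the time of their first treatment with cediranib or cediranib plus lenalidomide". It does not say when the window for the comparison ends. Section 5.3 sets no number of cycles; "treatment may continue until one of the following criteria applies", and the list that follows includes disease progression and "Unacceptable adverse events(s". On the expected course, Section 13.1.2 says "We therefore assume a median of 40 weeks for the cediranib alone arm" and sizes the trial to detect "a 75% improvement in the median to 70 weeks with combination therapy".

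The documents contain no exposure-adjusted rate, time-to-first-event analysis, common comparison window or significance level for adverse events. Section 5.1.2 adds that from April 10, 2015 Arm B patients stop lenalidomide and may stay on cediranib alone. Nothing says how their later events enter the comparison.

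**The concern.** A patient who is treated longer has more time in which to have a first adverse event. The trial is built to detect a longer time to progression in Arm B, and progression is a main reason for stopping. If the combination works as hoped, Arm B accumulates more affected patients even when lenalidomide adds no hazard. If the combination is poorly tolerated and stopped early, Arm B accumulates fewer, and a real excess can be hidden. A test on proportions cannot tell these situations from a true difference in toxicity. Toxicity is a named secondary objective (Section 1.3), and the randomised comparison is the trial's own evidence on what lenalidomide adds in harm.

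**Working it through.** **Inputs from the documents.** 36 and 74 patients; median PFS 40 and 70 weeks; PFS tested one-sided at 0.10 with 85% power; 1 year of accrual plus 1.5 years of follow-up (Section 13.1.2); 80 projected events (interim analysis paragraph of Section 13.1.2).

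**Assumptions not in the documents.** Exponential PFS; uniform accrual; time on treatment equal to PFS; no other dropout; a constant hazard *h* of first event, the same in both arms (range shown); a two-sided 5% level for the toxicity tests.

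**1. Reproduce the plan's figure.** Schoenfeld events = (1.2816 + 1.0364)² / [(36/110)(74/110)(ln 1.75)²] = 5.373 / (0.2202 × 0.3132) ≈ 78, against 80 stated.

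With λ = ln 2 / median, accrual A = 52.18 weeks and follow-up F = 78.27 weeks, the probability of a PFS event is P = 1 − [exp(−λF) − exp(−λ(A+F))] / (λA). This gives 0.830 in Arm A and 0.640 in Arm B. Expected events are 36 × 0.830 + 74 × 0.640 ≈ 77.3, and the patients needed are 78 / (77.3/110) ≈ 111, against 110 stated. The inputs therefore match the plan.

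**2. Implied exposure.** Mean time to progression or cut-off is P/λ: 47.9 weeks in Arm A and 64.7 weeks in Arm B, a ratio of 1.35.

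**3. Crude proportions with no true difference.** With k = λ + h, P(event) = (h/k) × {1 − [exp(−kF) − exp(−k(A+F))] / (kA)}. For h = 0.0183 per week this is 0.500 in Arm A and 0.612 in Arm B. Rejection by the chi-square test, from exact binomial enumeration with 36 and 74 patients:

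| Arm A affected | Arm B affected | Chi-square rejects |
|---|---|---|
| 10% | 13.3% | 6.3% |
| 20% | 26.2% | 9.9% |
| 30% | 38.5% | 13.5% |
| 50% | 61.2% | 20.1% |
| 60% | 71.2% | 22.4% |
| 70% | 80.0% | 22.6% |
| 90% | 94.0% | 12.1% |

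Nearly all rejections point against the combination (20.0 of the 20.1 points in the 50% row). Simulation that also counts events to 30 days after the last dose gives about 13%, 18% and 20% at 0.5, 1.0 and 1.5 events per patient-year.

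**4. Is exposure the cause?** With equal 40-week medians on treatment the crude test rejects in 4.9%. With 40 versus 70 weeks, an unstratified log-rank test on time to first event rejects in 5.3%, 4.8% and 5.5% when 30%, 50% and 70% of Arm A is affected.

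**5. Where it does not apply.** If risk is confined to the first 4 to 8 weeks, the arms differ by 0.4 to 1.6 percentage points and the crude test rejects in 5.0% to 5.6%. For risk over the first 26 weeks it rejects in 5.6% to 9.0%. Fisher's test, with 5% or 10% affected in Arm A, rejects in 1.8% and 3.9%.

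**6. The reverse direction.** If median time on treatment in Arm B is only 30 weeks, equal hazards give 50% versus 43.6%. Suppose instead that Arm B truly has 1.75 times the hazard, with 1.0 event per patient-year in Arm A and an Arm B median on treatment of 25 weeks (assumed). The crude test then finds the excess in about 9% of trials; a test that uses time at risk finds it in about 55%.

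**7. Choice of replacement.** A rate ratio on patient-years is not a safe substitute. With equal hazards confined to the first 8 weeks and 40 versus 70 week medians, it rejects in 17.8% of trials when 30% are affected and in 25.4% when 50% are. At 30%, almost all of these rejections wrongly show the combination as safer (median rate ratio 0.77). The log-rank test and an 8-week Fisher test stay at or below 5% in the same setting.

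**The case against.** The case for leaving the plan alone has four parts.

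- **Crude incidence is a legitimate estimand.** It describes the burden of a treat-to-progression strategy. This stands, and it is a reason to keep the crude table. It does not make the test informative about what lenalidomide adds per unit of time on treatment.
- **The figures rest on inputs that the plan does not give.** It states PFS medians, not treatment durations. Patients may stop for reasons other than progression, and under Section 6.2 lenalidomide is reduced when either agent could be responsible, so time on study is not lenalidomide exposure. This stands. The inflation belongs to the design alternative with a constant hazard and vanishes with equal exposure. Unequal stopping in the other direction does not rescue the test, however; it reverses the bias.
- **No decision hangs on these tests.** They have no stated significance level and no stopping rule; the futility rule uses conditional power for PFS. This stands and limits the importance of the point.
- **Onset dates may be missing.** Sections 5.5, 7.5 and 12.1 require a study-removal date and routine adverse-event reporting, but no requirement to record the onset date of every event was found. This stands as a condition on the fix.

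A reader might go further and infer that any toxicity difference the planned test reports is merely extra exposure. The documents do not support that. With no true difference the test stays non-significant in about 77% of trials or more, and a difference that is found may be a real effect of lenalidomide. Nor does the point extend to every toxicity: early-onset and rare events are essentially unaffected.

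**Conclusion.** The point holds as a limited one. For common toxicities that keep arising on treatment, the planned comparison cannot separate toxicity from exposure and can create or mask a difference. Under the design alternative and the assumptions listed, the false-positive rate per toxicity is up to about 4.5 times the nominal 5% (22.6/5), with a spurious difference of at most about 11 percentage points. The direction depends on actual time on treatment, which the plan does not predict. It would be wrong to infer that the PFS test, the sample size or the futility rule is affected; none of them uses these data. This is a modest improvement to a secondary safety analysis.

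**What to change.** Amend Section 13.4.2 as follows.

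1. Keep the table by type and grade, and crude incidence by arm, as description. Events per patient-year may be added, also as description only.
2. Base the between-arm comparison on (a) time to first event, from first dose to last dose plus 30 days, by a log-rank or Cox test stratified by prior VEGF-pathway inhibitor and performance status; and (b) the proportion affected through the end of cycle 2, by Fisher's exact test. Section 13.4.2 already uses the end-of-cycle-2 horizon for tumour size.
3. Do not use a constant-hazard rate ratio as the test, for the reason in step 7 of the working.
4. State how Arm B events and time after April 10, 2015 are counted, for example by censoring at the lenalidomide stop, with a sensitivity analysis that includes the later period.

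The cost is plan wording and one more table, with no new patients or visits. The downsides are two toxicity summaries to explain instead of one, and the need to confirm that adverse-event onset dates are available. If they are not, (a) cannot be run, and (b) needs at least the cycle in which each event began.

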Prior to the randomized phase II portion of this study, we will evaluate cediranib plus lenalidomide in a phase I trial at three dose levels of lenalidomide (10, 15, and 20 mg). Cediranib will be administered at a starting dose of 20 mg daily. Dose escalation will not exceed 30 mg cediranib with 20 mg of lenalidomide. The MTD from the Phase I was determined at cediranib 30 mg day 1-28 and lenalidomide 15 mg on day 1-21 of the 28 day cycle.

After determining the MTD, we will initiate recruitment for a Phase II trial comparing cediranib alone to cediranib plus lenalidomide. Subjects will be randomized in a 1:2 ratio to one of two arms. Randomized stratification will employ prior therapy with a VEGF-pathway inhibitor (yes vs. no) and performance status (0 and 1 vs. 2). Subjects in Arm A will receive cediranib alone at 30 mg daily. Subjects on Arm B will receive cediranib 30 mg daily and lenalidomide 15 mg on day 1-21 of the 28 day cycle (as determined above in the Phase I trial).

Each cycle will be 4 weeks in length. Disease re-evaluation will occur every 8 weeks using RECIST guidelines.* The primary endpoint will be progression-free survival. Patients without evidence of anti-thyroglobulin antibodies will continue to have thyroglobulin levels measured at each response assessment (usually every 8 weeks). All patients are expected to be on thyroxine suppression therapy and thyroid stimulating hormone (TSH) levels will be monitored pre-therapy and every 8 weeks.

*After 18 cycles, radiologic disease re-evaluation will occur every 16 weeks.

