A number of events of bleeding and hemorrhage have occurred. Some events of hemorrhage were fatal but causality could not be unequivocally assigned to cediranib. Gastrointestinal perforation, sometimes associated with fistula formation, has been observed in patients receiving cediranib. Some events of gastrointestinal perforation have been fatal but causality could not be unequivocally assigned to cediranib.

Fatigue, hand and foot syndrome, diarrhea, headache, nausea, vomiting, anorexia and weight loss are commonly occurring AEs in cediranib studies. Dehydration has been observed in clinical studies as a consequence of cediranib-related or chemotherapy-related diarrhea, vomiting, anorexia, or reduced oral intake.

Hoarseness (dysphonia) has been reported as common and dose-related.

Muscle weakness, proteinuria, dry mouth and oral mucosal inflammation have been observed in cediranib studies.

Reversible posterior leukoencephalopathy syndrome (RPLS) has been observed in patients receiving cediranib in clinical studies. RPLS is a rare syndrome affecting vascular endothelial cells in the brain that may lead to capillary leak and edema. It has been associated with a number of conditions, including renal failure, hypertension, fluid retention, and the use of cytotoxic or immunosuppressive drugs. RPLS also been reported in association with the use of VEGF inhibitors including bevacizumab, sunitinib, and sorafenib.

Increases in transaminases, which are sometimes associated with increases in total bilirubin, have been seen. Thrombocytopenia, of CTC Grade 1 or 2 in the majority of cases, has been seen with monotherapy and combination cediranib treatment. In addition, cediranib has been associated with increases in TSH which may be associated with clinical hypothyroidism.

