2.4.2. Plasma

TSH and thyroglobulin measurements will be performed at the respective institution of the enrollee. TSH can stimulate thyroid cancer growth. Participants will have TSH measured pretherapy and every 8 weeks to assess for adequate TSH suppression. Thyroglobulin serves as a tumor marker in thyroid cancer. It is not always reliable because some patients have anti-thyroglobulin antibodies that falsely alter the thyroglobulin measurement and because some advanced cancers lose the ability to make thyroglobulin effectively. However, in patients with cancers that make thyroglobulin, this protein can serve as a useful surrogate of targeted agent activity. Patients who do not have anti-thyroglobulin antibodies will have thyroglobulin measurements pretherapy and at 8 week intervals.

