		Hepatic failure	
INFECTIONS AND INFESTATIONS			
	Infection ⁴		
INJURY, POISONING AND PROCEDURAL COMPLICATIONS			
		Wound complication	
INVESTIGATIONS			
	Alanine aminotransferase increased		Alanine aminotransferase increased (Gr 3)
	Alkaline phosphatase increased		
	Aspartate aminotransferase increased		Aspartate aminotransferase increased (Gr 3)
	Lymphocyte count decreased		

Adverse Events with Possible Relationship to Cediranib (AZD2171) (CTCAE 5.0 Term) [n= 1608]			Specific Protocol Exceptions to Expedited Reporting (SPEER)
Likely (>20%)	Less Likely (<=20%)	Rare but Serious (<3%)	
	Neutrophil count decreased		
	Platelet count decreased		
	Thyroid stimulating hormone increased		Thyroid stimulating hormone increased (Gr 2)
	Weight loss		Weight loss (Gr 2)
METABOLISM AND NUTRITION DISORDERS			
Anorexia			Anorexia (Gr 3)
	Dehydration		Dehydration (Gr 3)
	Hypophosphatemia		Hypophosphatemia (Gr 3)
MUSCULOSKELETAL AND CONNECTIVE TISSUE DISORDERS			
	Generalized muscle weakness		
NERVOUS SYSTEM DISORDERS			
	Dizziness		Dizziness (Gr 2)
	Headache		Headache (Gr 3)
	Lethargy		
		Leukoencephalopathy	
		Reversible posterior leukoencephalopathy syndrome	
RENAL AND URINARY DISORDERS			
		Nephrotic syndrome	
	Proteinuria		Proteinuria (Gr 2)
RESPIRATORY, THORACIC AND MEDIASTINAL DISORDERS			
	Cough		Cough (Gr 2)
	Dyspnea		Dyspnea (Gr 3)
	Laryngeal mucositis		Laryngeal mucositis (Gr 2)
	Pharyngeal mucositis		Pharyngeal mucositis (Gr 2)
	Tracheal mucositis		Tracheal mucositis (Gr 2)
Voice alteration			Voice alteration (Gr 2)
SKIN AND SUBCUTANEOUS TISSUE DISORDERS			
	Palmar-plantar erythrodysesthesia syndrome		Palmar-plantar erythrodysesthesia syndrome (Gr 2)
VASCULAR DISORDERS			
		Arterial thromboembolism	
Hypertension			Hypertension (Gr 3)
	Thromboembolic event		Thromboembolic event (Gr 4)
	Vascular disorders - Other (hemorrhage) ⁵		

¹This table will be updated as the toxicity profile of the agent is revised. Updates will be distributed to all Principal Investigators at the time of revision. The current version can be obtained by contacting [contact]. Your name, the name of the investigator, the protocol and the agent should be included in the e-mail.

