- f: Pregnancy tests for females of childbearing potential. A female of childbearing potential (FCBP) is a sexually mature female who: 1) has not undergone a hysterectomy or bilateral oophorectomy; or 2) has not been naturally postmenopausal for at least 24 consecutive months (i.e., has had menses at any time in the preceding 24 consecutive months).
- g: Pregnancy tests must occur within 10 – 14 days and again within 24 hours prior to initiation of lenalidomide. FCBP with regular or no menstruation must have a pregnancy test weekly for the first 28 days and then every 28 days while on therapy (including breaks in therapy); at discontinuation of lenalidomide and at Day 28 post the last dose of lenalidomide. Females with irregular menstruation must have a pregnancy test weekly for the first 28 days and then every 14 days while on therapy (including breaks in therapy), at discontinuation of lenalidomide and at Day 14 and Day 28 post the last dose of lenalidomide (see Appendix H: Lenalidomide Risks of Fetal Exposure, Pregnancy Testing Guidelines and Acceptable Birth Control Methods).
- h: The Lenalidomide Education and Counseling Guidance Document (Appendix I) must be completed and signed by a trained counselor at the participating site prior to each dispensing of lenalidomide treatment. A copy of this document must be maintained in the patient records. The Lenalidomide Information Sheet (Appendix J) will be given to each patient receiving lenalidomide treatment. The patient must read this document prior to starting lenalidomide study treatment and each time they receive a new supply of study drug.
- i: Pre-study, all patients with 1+ protein reading or greater on urinalysis should collect a 24 hour urine collection to measure protein. During the study, patients with 2+ or greater proteinuria should collect a 24 hour urine collection to measure protein. Study medication should be held until 24 hour urine collected and evaluated. See Section 6.2 for dose modification.
- j: Archival tissue should be requested pre-study but should not delay the start of therapy.
- k: Study calendar can vary +/- 3 days without a study violation.
- l: Radiology evaluation repeated every 2 cycles. Subjects on protocol 18 months or more will have radiology evaluation every 4 cycles.
- k: Off-study evaluation.
- m: TSH and thyroglobulin evaluation repeated every 2 cycles.
- n: After 12 months on study, subjects can be evaluated every 2 cycles.

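### RM ANOVA is named for serial TSH and thyroglobulin with no method for series cut short at progression, and the hypothesised TSH decrease runs against the protocol's own text

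*Combined protocol and SAP*

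**What the plan says.** Section 13.4.2 (Phase II secondary endpoints) covers both markers in two sentences: "Repeated measures analysis of variance (RM ANOVA) will be performed to determine the effect of the treatments on serial measurements of TSH and thyroglobulin", followed by "It is hypothesized that these levels will decrease over time". It gives no visit window, covariance structure, transformation or rule for incomplete series.

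Section 2.4.2 gives the two markers different purposes. Thyroglobulin is a tumour marker and possible surrogate of drug activity, measured in a subset: "Patients who do not have anti-thyroglobulin antibodies will have thyroglobulin measurements pretherapy and at 8 week intervals". TSH is a check on background treatment: "Participants will have TSH measured pretherapy and every 8 weeks to assess for adequate TSH suppression". Section 2.1 adds: "All patients are expected to be on thyroxine suppression therapy".

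On the schedule, a footnote to the Section 10 calendar says "TSH and thyroglobulin evaluation repeated every 2 cycles", and the calendar also marks both tests at pre-study and off-study. Under Sections 5.3 and 5.5, patients leave study at progression, intercurrent illness, unacceptable toxicity, withdrawal or on the investigator's judgment.

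On the direction of TSH, the safety profile in Section 2.2.1 states that "cediranib has been associated with increases in TSH which may be associated with clinical hypothyroidism". The cediranib risk list in Section 7.1.1 includes raised TSH and hypothyroidism, each in the category of 20% or less. Both Phase II arms receive cediranib.

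**The concern.** There are two separate issues.

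**Selection.** Classical RM ANOVA needs a value at every visit in the window and drops patients with gaps. Here the regular series ends mainly because the disease progresses, and a rising thyroglobulin plausibly precedes progression. The patients left are then those whose marker behaved best. If the combination delays progression, the arms are also thinned at different rates. A fall in thyroglobulin is what the plan hypothesises, so selection would push the result towards the expected answer.

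**TSH direction.** One hypothesis of decrease covers both markers. It suits thyroglobulin. For TSH, the protocol reports increases on the drug given in both arms, and it measures TSH to confirm suppression, not to detect activity. A TSH finding would be read against an expectation that no section supports.

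**Working it through.** **1. The plan's own figure.** The RM ANOVA has none. The PFS medians that set the drop-out rates come from Section 13.1.2, so that design was checked first. With one-sided alpha 0.10, 85% power, hazard ratio 1.75 and 36:74 allocation, the Schoenfeld formula gives

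events = (1.2816 + 1.0364)² / [(36/110)(74/110)(ln 1.75)²] = 5.373 / (0.2202 × 0.3132) ≈ 78,

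against 80 projected. The design reproduces.

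**2. Who is still in the regular series.** With exponential PFS, the share progression-free at week t is 0.5^(t/median), with medians of 40 weeks (A) and 70 weeks (B).

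| Week | A (of 36) | B (of 74) | Total (of 110) | Ratio B/A |
|---|---|---|---|---|
| 8 | 87% (31.3) | 92% (68.4) | 99.7 | 1.06 |
| 16 | 76% (27.3) | 85% (63.2) | 90.4 | 1.13 |
| 24 | 66% (23.8) | 79% (58.3) | 82.1 | 1.20 |
| 40 | 50% (18.0) | 67% (49.8) | 67.8 | 1.35 |
| 48 | 44% (15.7) | 62% (46.0) | 61.7 | 1.43 |

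These counts are upper limits. Toxicity and withdrawal also end the series, and thyroglobulin is measured only in antibody-negative patients, whose share is not given.

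**3. How large the artefact could be.** The inputs in this step are assumptions, not protocol figures:
- the true mean change in log thyroglobulin is zero in both arms;
- the SD of individual slopes is 0.4 log units per 40 weeks, and the residual SD is 0.3;
- the progression hazard is multiplied by exp(θ) per SD of slope u.

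The mean log change among week-40 completers is 0.4 × E[u·S(u)] / E[S(u)], where S(u) = exp(−ln 2 × (40/median) × e^(θu)) and u is standard normal.

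| θ | Fall, A | Fall, B | Arm difference (log) |
|---|---|---|---|
| 0 | 0% | 0% | 0 |
| 0.35 | 9% | 5% | 0.04 |
| 0.7 | 16% | 11% | 0.06 |
| 1.0 | 20% | 14% | 0.07 |

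At θ = 0.7 the log changes are −0.173 (A) and −0.112 (B), so 1 − e^(−0.173) = 16%, 1 − e^(−0.112) = 11%, and the difference is 0.061. Rescaling the hazards to hold the medians at 40 and 70 weeks gives 15% and 10%.

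Arm A is the more heavily selected, so it shows the larger false fall and the combination looks worse. The arm difference had an SD of about 0.13 across simulated trials of this size, so the bias is 0.06/0.13, or about half a standard error.

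**4. What a mixed model recovers.** With the same inputs and θ = 0.7, a random intercept and slope model was fitted to all values up to week 40 in 60 simulated trials. It still showed false falls of about 11% (A) and 7 to 8% (B) and an arm difference of 0.03 to 0.05. Adding a value at exit left these figures within simulation error. Drop-out tied to the latent slope is not missing at random, so the mixed model removes only part of the bias.

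**5. TSH.** Section 13.4.2 expects a decrease. Sections 2.2.1 and 7.1.1 report increases. Section 2.4.2 measures TSH to check suppression, and Section 2.1 expects every patient to be on thyroxine. No section gives a reason to expect TSH to fall.

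**The case against.** A reader might infer that the plan analyses only patients who stay progression-free. The documents do not say so. They state no complete-case rule and no window, and the term RM ANOVA is sometimes used for a likelihood-based model that keeps partial series. What stands is that the method for incomplete series is missing and that the standard reading of the named method is the unfavourable one. The off-study draw is a real mitigation. It supplies one value at exit, but it does not fill the missed scheduled visits that a complete-series analysis requires.

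Week 40 is a choice made for illustration. A window ending at week 8 or 16 would lose far fewer patients, so the size of the problem depends on a window that the plan does not set. The simulated percentages rest on assumed inputs and vanish if thyroglobulin slope and progression are unrelated.

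It is also tempting to say that the protocol refutes a TSH decrease, or that the plan tests for one. Neither is supported. The safety text reports an association, and the risk list puts raised TSH at 20% of patients or fewer, so neither fixes a mean change. Section 13.4.2 specifies no one-sided test here, and the RM ANOVA F test is non-directional: it would detect a rise as readily as a fall. The fault is in the stated expectation, not in the error rate.

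Finally, the stakes are low. Neither marker appears among the secondary objectives in Section 1.3.

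**Conclusion.** The point holds as a gap in specification with a foreseeable bias. The plan names a method whose classical form would rest on about 50% of Arm A and 67% of Arm B at week 40, a share that follows from its own medians and exponential PFS. The direction of the bias follows if rising thyroglobulin goes with earlier progression: a false fall in both arms, larger in A, so the spurious arm difference counts against the combination. A reader might fear a manufactured benefit for Arm B; under the planned PFS advantage and the same link in both arms, the artefact runs the other way. The roughly 11 to 16% fall and 6% arm difference are illustrative only, and the arm difference is small beside its standard error.

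The decrease hypothesis is reasonable for thyroglobulin and runs against the protocol's own text for TSH. The primary PFS test, the sample size and the power are not touched.

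**What to change.** In Section 13.4.2:

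- **Thyroglobulin.** Replace RM ANOVA with a linear mixed model (random intercept and slope) on log thyroglobulin in antibody-negative patients. Use every available value, including the off-study draw, with arm, time, arm-by-time and the two stratification factors. State the time window and the covariance structure.
- **Sensitivity.** Add a joint model of log thyroglobulin and PFS. Because the mixed model removes only part of the bias, state that no conclusion will be drawn from it alone, and report the number contributing at each visit by arm.
- **TSH.** Analyse log TSH separately as a suppression and safety measure, and remove it from the hypothesis of decrease.

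The cost is a few sentences of text and slightly more programming. No new data or visits are needed. If RM ANOVA was meant as a likelihood-based model from the start, saying so settles the choice of model, but the window, the sensitivity analysis and the TSH wording still need to be written.
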